present nursing leadership which place a high value on holistic and person center care that is congruent with the Inova mission and values and strategic plan. The emphasis on holistic care has been supported by a Holistic Council which includes over 100 members from across the Inova Health Care System. The Chief Nurse Executive appointed two co- chairs: a doctoral prepared nurse and clinical bedside nurse. Inova nurses and researchers have conducted 5 studies on healing touch to date with positive outcomes for patients^{14 15} and for nurses.^{16 17} There are 538 nurses at Inova who have received Healing Touch training. In summary, Inova is able to support a Healing Touch study given the culture, support by leadership and the availability of nurses trained in Healing Touch. This research will build on previous HT studies conducted at Inova to assist the research team in understanding the impact of HT on patient-centered and patient-reported outcomes. This is the first study with HT being conducted on post-cesarean patients.

2. STUDY DESIGN AND SUBJECT SELECTION

2.1. Study Type

Experimental: Randomized Control Trial

2.2. Setting/Location

The intervention will take place during the postpartum stay. Participants in the HT intervention groups and control groups will be recruited from: Inova Loudoun Hospital (ILH),

Inova Alexandria Hospital (IAH), Inova Fair Oaks Hospital (IFOH), Inova Fairfax Medical Campus (IFMC).

2.3. Duration of Study

The study intervention lasts approximately 15 minutes. Women will participate in the study during their postpartum stay after cesarean section, which may last between two and six days. They will receive one intervention or control session during their stay.

2.4. Number of Subjects

The total number of subjects expected to participate will be 160. Sample size estimates require a sample of 128 women, but to obtain an adequate sample size there will be an oversampling of up to 160 subjects, 40 at each study site.

2.5. Study Population

2.5.1.Gender of Subjects

Female

2.5.2.Age of Subjects

Study participants will be 18 years of age or older. The typical age range of persons undergoing cesarean delivery is 18 to 45 years of age.

2.5.3.Racial and Ethnic Origin

Within the limitations imposed by the population of the study sites, persons of diverse racial/ethnic backgrounds will be recruited equitably. The study limitations exclude women who are not English speaking. This is because of the limited number of Healing Touch practitioners available who speak a language other than English. Speaking with subjects is an integral part of the Healing Touch therapy session. The effectiveness of Healing Touch when there is a language difference between the subject and the practitioner has not been evaluated. Therefore for the fidelity of the study intervention only English speaking subjects will be recruited at this time. However, the study will equitably recruit English speaking subjects, which will allow for ethic and racial diversity within the eligible group of potential study subjects.

2.5.4. Vulnerable Populations

The women will be recruited for the study while they are pregnant, and are therefore a vulnerable population. However, the study intervention takes place after delivery, when they are no longer considered a vulnerable group. The women randomized into the intervention group will have recently undergone surgery, and may have received narcotic medications for pain control during and after surgery. To account for this vulnerable state, the research team will be consenting subjects for the study prior to surgery. Because the study sample criteria excludes women under the age of 18 years, there will be no children included in this study.

2.6. Recruitment

Obstetrical offices will distribute a Healing Touch informational brochure to their scheduled cesarean patients. Study personnel will look at the schedule for the operating room at their facility. Patients with a scheduled cesarean delivery at ILH, IAH, IFOH, IFMC will be introduced to and informed of the study by a member of the study team via a phone call or email 1-2 weeks prior to their cesarean date (Appendix H). The email includes an overview of the study with a link for the electronic consent form (Appendix I). Questions

may be submitted via email or direct phone call to the principal investigator. Participants who complete the electronic consent form have the potential to be enrolled in the study and randomized into either the intervention or control group. The email containing the link for study consent will also include contact information for the study PI. Therefore, if at any time prior to cesarean delivery the woman changes her mind about her consent she can contact the study team to redact her consent. If a participant does not complete the HIPPA authorization form or the consent form prior to their scheduled c-section date, a copy of the consent form will be offered to them when they sign in for their surgery by a research team member. If they are still interested in participating in the study, they can sign the hard copy of the consent or HIPAA then.

2.7. Inclusion Criteria

- (1) the ability to ensure informed consent and completion of study assessments
- (2) the ability to speak, read, and understand English
- (3) scheduled cesarean delivery
- (4) ≥ 18 years of age

2.8. Exclusion Criteria

- (1) Non-English speaking due to the fidelity and variability of the research
- (2) Prisoners
- (3) Isolation precautions
- (4) active psychosis and impaired cognition
- (5) cesarean delivery who delivers prior to scheduled cesarean date

3. STUDY METHODS AND PROCEDURES

3.1. Study Treatment/Intervention

If the woman completes the consent form, they will be enrolled in the study and randomized into either the intervention or control group. When they are admitted to the postpartum unit after cesarean delivery, based on their randomization, the study coordinator at each site will schedule either 1) a Healing Touch (HT) practitioner for the intervention group OR 2) a non-HT practitioner who will collect data for the control group. The HT practitioners for this study will be registered nurses or HT practitioners who work in the Inova Health System and have received the minimum of Foundations of Healing Touch training. All study personnel entering patient care areas will abide by universal precautions, plus masks and face shields as required by the hospital system for infection control. For the intervention group, the HT practitioner will verify consent. Then they will ask the woman to complete baseline measurements of pain and anxiety. The practitioner will then administer the HT intervention consisting of a full body, pain management technique focusing on the surgical site, and wound sealing. HT techniques (Field Repatterning, Pain Syphon, Beak Fingers Lasering,) are techniques specific to management of pain and clearing of the energy field that have been used frequently by the nurses in their delivery of patient care. The HT intervention to be used in the proposed study has been developed by co-investigator, [name], Certified Healing Touch Practitioner and Instructor, to focus on the symptom management needs of the study participants (post-cesarean delivery) and should take no more than 15 minutes to complete. Levels of pain and anxiety will be reassessed post-intervention. Nurses providing the HT intervention will document the session and other outcomes as described below. There is a risk that the patient will not receive Healing Touch if: there is not a HT provider available or the patient is discharged prior to availability of the HT provider.

Privacy will be maintained during the consenting process by calling potential study subjects on their personal phone number. During consent, the script will prompt the study personnel getting consent to ask if this is a good / safe time to speak. If not, the study personnel will call at a better time for the potential study subject. During the intervention (or control activity), the study personnel will first confirm that the study subject provided consent, and will confirm consent. They will be prompted to provide privacy for the woman when needed or requested by the study subject before the intervention begins. The intervention study personnel will confirm that they can place a "do not disturb" sign on the door of the study subject before they begin the study intervention, because the sign may indicate that the subject is receiving the intervention and may be a privacy concern for the subject. The study

personnel will also confirm that any family members or visitors at the bedside should stay or leave during the intervention, to maintain subject privacy.

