Study Methodology: One to two weeks prior to a scheduled cesarean delivery, a member of the research team will call and screen women for eligibility on the study. If the woman electronically completes the consent form, they will be enrolled in the study and randomized into either the intervention or control group. Based on their randomization, the study coordinator at each site will schedule either 1) a Healing Touch (HT) practitioner for the intervention group OR 2) a non-HT practitioner who will collect data for the control group, and complete demographic information from the participant's medical chart. For the intervention group, the HT practitioner will verify consent, then ask the woman to complete baseline measurements of pain and anxiety. The practitioner will administer the HT intervention. Levels of pain and anxiety will be reassessed post-intervention. For the control group: a member of the research team, will ask the woman to complete baseline measurements of pain and anxiety. The subject will then be encouraged to have 15 minutes of quiet time, with the lights dimmed. After the 15 minutes of quite time, the team member will again measure the subject's levels of pain and anxiety.

Statistical Methodology: Descriptive and inferential statistical techniques will be used to determine differences between the intervention and control groups.

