3.2. Control Group

This study has a control group. For the control group: a member of the research team, who may or not be a HT practitioner, will verify consent. Then they will ask the woman to complete baseline measurements of pain and anxiety. The subject will then be encouraged to have a quiet time session equivalent to the length of a Healing Touch session, with the lights dimmed. After the quite time, the team member will again measure the subject's levels of pain and anxiety.

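### The sections disagree on when women are allocated, and women whose Healing Touch session stops for worsening pain can drop out of one arm with no stated handling

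*Combined protocol and SAP*

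**What the plan says.** **Timing of allocation.** The abstract states "If the woman electronically completes the consent form, they will be enrolled in the study and randomized into either the intervention or control group", one to two weeks before surgery. Section 3.1 says "If the woman completes the consent form, they will be enrolled in the study and randomized into either the intervention or control group", and section 3.5 agrees in substance. Section 3.1 then continues: "When they are admitted to the postpartum unit after cesarean delivery, based on their randomization, the study coordinator at each site will schedule" the session for the allocated arm. Section 2.6 is softer ("Participants who complete the electronic consent form have the potential to be enrolled in the study and randomized") and lets late signers complete the form on the day: "a copy of the consent form will be offered to them when they sign in for their surgery".

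Section 4.3.1 defines enrolment as a set of conditions that must all be met: forms returned, consent confirmed by an investigator, investigator signature, renewed eligibility screen and, listed last, assignment to a study intervention. Women who have only a completed form are to be logged under a reason (no provider, criteria not met, early delivery).

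**Ways a woman can be lost.** Section 2.8 excludes a "cesarean delivery who delivers prior to scheduled cesarean date". Section 3.5 re-checks consent just before the session. Section 3.1 warns: "There is a risk that the patient will not receive Healing Touch if: there is not a HT provider available" or she goes home first. Section 4.3.1 says a provider shortage can prevent either kind of session. Section 3.6 allows withdrawal at any time, but lists reasons to stop a session and withdraw the woman for the HT session only. One of them is increased pain for which she needs help.

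**Analysis.** Section 4.2 gives an independent-samples t-test on pain and anxiety, with assumption checks and a Welch fallback. It names no analysis set and no rule for a missing post score.

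**The concern.** A woman who completes the form and then delivers early is a randomised participant under the abstract, 3.1 and 3.5, but was never enrolled under 4.3.1. Until one order is fixed, the denominator of the trial is undefined, and who belongs in it could be settled after scores have been seen.

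The more serious matter is a loss tied to both arm and outcome. Pain is a primary outcome, measured just before and just after a session of about 15 minutes. A woman whose pain rises enough for the HT session to be stopped is withdrawn. If her post score is not collected, a t-test on available scores omits her. No stated rule removes a worsening woman from quiet time. The HT mean would then look better than it is.

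**Working it through.** **1. The sections side by side.**

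| Event before the session | Allocation at form completion (abstract, 3.1, 3.5) | Assignment last (4.3.1) |
|---|---|---|
| Form completed, nothing further | Randomised | Not enrolled |
| Early delivery | Loss after allocation, both arms | Can be logged before assignment |
| Consent re-check at the session (3.5) | Loss after allocation, both arms | Still after assignment, unless assignment waits until then |
| No provider | Loss after allocation; HT only per 3.1 | Can block either session |
| Discharge first | Loss after allocation; stated for HT only | Not addressed |

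How a shortage could block quiet time is itself unclear. Section 3.2 says it is run by "a member of the research team, who may or not be a HT practitioner, will verify consent", while the abstract and 3.1 specify someone who is not an HT practitioner. These too must be reconciled.

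**2. Inputs.** From 4.1: two-sided alpha 0.05, d = 0.5, 64 per arm, 160 recruited, equal allocation intended (so 80 per arm). Loss counts and score differences below are my assumptions; the documents give none.

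**3. The plan's own figure.** Power uses the noncentral t with n1 + n2 - 2 degrees of freedom and λ = d / √(1/n1 + 1/n2). At 64 per arm, λ = 0.5 / √(2/64) = 2.828 and power is 0.8015, so 128 reproduces. Since 128 / 0.80 = 160, the oversample equals a 20% loss allowance.

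**4. Power.** At 80 per arm, λ = 0.5 / √(2/80) = 3.162 and power is 88.2%. Averaged over Binomial(160, 0.5) coin-flip splits it is 88.0%. An exact 80:80 split has probability 6.3%.

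**5. Type I error when stopped HT sessions leave no post score.** Suppose k of 80 HT women are lost and their mean change is δ SD worse than that of the HT women scored. With no true effect, the scored HT mean is too favourable by (k/80)δ, and λ = (k/80)δ / √(1/(80 - k) + 1/80).

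| k | δ (SD) | Bias (SD) | λ | Type I error |
|---|---|---|---|---|
| 2 | 0.5 | 0.0125 | 0.079 | 5.1% |
| 2 | 1 | 0.025 | 0.157 | 5.3% |
| 4 | 0.5 | 0.025 | 0.156 | 5.3% |
| 4 | 1 | 0.05 | 0.312 | 6.1% |

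If the women lost are exactly the k worst scorers of 80, simulation with normal scores and no true effect gives about 7% at k = 2 and about 11% at k = 4.

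**6. Equal loss rates are not a safeguard.** Let 16 of 80 be lost in each arm, with lost HT women 0.5 SD worse and lost controls no different from those who stay. Bias = 0.20 × 0.5 - 0.20 × 0 = 0.10 SD; λ = 0.10 / √(2/64) = 0.566; type I error is 8.7%. At 8 of 80 in each arm it is 6.0%. It returns to 5% only if the lost women differ by the same amount in both arms, or not at all.

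**7. How far a positive result could be pushed.** Take an observed difference of 0.5 SD with 16 of 80 HT scores missing. Imputing them Δ SD worse moves the estimate to 0.5 - 0.20Δ. By multiple imputation the standard error is about 0.172. At Δ = 0.80 the ratio is 0.34 / 0.172 = 1.98 (p just under 0.05); at Δ = 0.85 it is 0.33 / 0.172 = 1.92 (p just over). Significance is lost just above 0.8 SD. With 4 missing, it takes about 3 SD.

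**The case against.** The best defence is that 4.3.1 is the operative definition and the one-line statements elsewhere are shorthand. Section 2.6 says only that form completers may be enrolled, and 3.5 calls consent a two-step process; both fit 4.3.1. Its conditions are not described as a time sequence, it uses a word for assignment rather than randomisation, and it already logs early losses by reason. Much of this stands, and one clarifying sentence might settle the order. But 4.3.1 describes women who have a completed form and have taken no further step, which cannot be squared with randomisation on form completion. Nor does listing assignment last place it after delivery: 4.3.1 and 5.4 schedule sessions by the planned delivery date.

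Three stronger readings are tempting, and the documents support none of them.

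- *Provider shortage biases the result.* Losing 20% of HT women only, each 0.5 SD worse, would give a type I error of 9.1% (64 v 80). No section links shortage or early discharge to a worse change over one session, and 4.3.1 says shortage can stop either session.
- *Type I error could reach about 63%.* That requires exactly the worst 20% of HT scorers to vanish. It is a mathematical extreme, not a description of this plan.
- *The post score is skipped after a stopped session.* Section 3.6 does not say so. It says the woman is withdrawn and is silent on the score.

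The coin flip is not a power problem either: it costs 0.2 percentage points (88.2% to 88.0%).

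**Conclusion.** The point holds and should be fixed. The timing statements conflict and must be reconciled. Section 3.6 can remove worsening women from the HT arm alone on a primary outcome, and section 4.2 does not say how they are handled.

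The size is unknown. For the one route with a stated link to worsening, an assumed 2 to 4 of 80 HT women without a post score gives a type I error of 5.1-6.1% if they are 0.5-1 SD worse, and about 7-11% if they are the worst scorers. This rests on 80 allocated per arm, no true effect, no related loss in quiet time, and the post score not being taken. Losses unrelated to change in score give no bias, and early delivery and the consent re-check may well be of that kind. Similar loss rates in the two arms would not by themselves be reassuring (8.7% in the example above). The sample size and power are sound.

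**What to change.** 1. **One order, stated identically** in the abstract, 2.6, 3.1, 3.5, 4.3.1 and 5.4. Allocate on the postpartum unit, after delivery on the scheduled date and re-confirmed eligibility and consent, immediately before the session is booked. Section 3.1 already books at that point. Log earlier losses, with reason, as not randomised. Confirming a free HT provider before allocation is optional: it would hold a slot for all 160 women instead of about 80, that is 80 × 15 minutes = 20 hours of extra slots.
2. **A pre-generated, concealed list**, in blocks of varying size by site, in place of a coin flip by study staff. The gain is concealment and the equal allocation that 4.1 states, not power.
3. **Leave the stopping criteria as they are**, but separate a stopped session from withdrawal from data collection. In both arms, take the post score when a session stops, if the woman agrees, and record the time.
4. **Analysis.** Analyse all randomised women with scores in their allocated arm, and report losses by arm and reason. Add a multiple-imputation sensitivity analysis for pain and for anxiety, shifting missing change scores towards worse separately by arm (for example 0 to at least 1 SD in steps of 0.25), and report where the conclusion changes.

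Cost: one amendment, one list and a short analysis paragraph, with shorter notice for booking after delivery and a little more analysis work. Late allocation narrows the HT-only losses from shortage and discharge but does not remove them; item 4 covers what remains. The target stays at 128, recruiting 160.

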3.4. Endpoints/Outcomes Measurements

3.4.1.Primary outcomes.

Primary outcomes will include the differences between the intervention and control groups' pre-/postintervention levels of pain (Numeric Rating Scale) and anxiety (Numeric Rating scale) (Appendix K).

Theoretical Concept and Measurement	#	Score	Reliability
	Items	Range	
Demographics			
As delineated in Data Retrieval Form	12		
Pain (Primary outcome)			
Visual Analog Scale: Measures pain intensity. Higher scores indicate higher levels of pain	1	0-10	* r =0.96 literate patients r= illiterate
Anxiety (Primary outcome)			
Hospital Anxiety Scale: Measures intensity of anxiety. Higher scores indicate higher levels of anxiety	16	0-14	Cronbach's alpha 0.73**
Healing Touch			-

* (Hawker, Mian, Kendzerska, & French, (2011). * Ferraz., Quaresma, Aquino, Atra, Tugwell, P., & Goldsmith, 1990).

**Al Aseri, Suriya, Hassan, Hasan, Sheikh, Al Tamimi, Alshathri M, Khalid N. (2015).

3.4.2.Secondary outcomes

Secondary outcomes include the relationship between HT and demographic information of the subjects. As well, the feasibility of introducing HT as a therapy for postpartum women will be assessed.

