3.5. Consent/Assent

All participants in the HT intervention group and control group will provide informed consent. Acquiring consent is a twostep process: (1) Participant returning and electronic consent via the survey platform, and then (2) the site PI/SUB-I has a conversation with the participant over the phone or face to face to review the consent. Once screened for eligibility, a member of the research team may call the potential participant using the consent phone call script (Appendix H). Whether over the phone or face to face, the study personnel will describe the study, answer any questions they may have, and if the participant is interested, email them an electronic consent form and the HIPPA authorization form if they haven't already received one. Both of these forms will be managed through an electronic platform, and securely load into the platform to be accessed by

the PI and study personnel. Participants who complete the electronic consent form will be included in the study, and randomized into either the intervention or control group. Informed consent will be confirmed again with the women prior to starting the study intervention or control session, since they may have changed their mind after delivery. One copy of the consent and HIPAA forms will be given to the participant (via email or face to face), and one will be kept in the research file for the participant, as well as being scanned into the electronic medical record.

3.6. Monitoring Subjects and Criteria for Withdrawal of Subjects from the Study.

Study participants may voluntarily withdraw from the study at any time. During the Healing Touch Therapy, the intervention would stop and a subject would be withdrawn if: The woman or her family at the bedside requested the intervention stopped, the woman reported an increase in pain and needs assistance, the woman had a self-identified change in clinical status and requested medical assistance, the woman needs to stop the session to care for the baby or get out of bed / leave the room for some reason.

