The study Sub-Investigators at each site will follow the same procedure. Once a potential study subject has been enrolled in the study they will receive a coded study "ID" which will consists of numbers and letters. Any data collected during the study will be coded with this study ID. After being randomized into the intervention group or control group, and based on their scheduled delivery date, the study site coordinator will schedule the subject for either a session with a Healing Touch practitioner, or a session of quiet time (the control) with a member of the study team. The Demographic Form (Appendix D) and Data Collection Form (Appendix K) will be labeled with the patient identification sticker. This is to ensure that study personnel can use the sticker to accurately identify study subjects. After the data is collected from the session, the form will be put into a sealed envelope and given directly to the study site coordinator. The site coordinator will enter the data from the subject into the spreadsheet with the coded ID. This coded data will be shared securely with the study Primary Investigator, who will synthesize the data from the various study sites.

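### Baseline pain and anxiety are self-reported after randomization to the arm-aware person who runs the session, and nothing keeps the arm from the woman until they are recorded

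*Combined protocol and SAP*

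**What the plan says.** Allocation comes first. Section 3.5 states: "Participants who complete the electronic consent form will be included in the study, and randomized into either the intervention or control group". By the abstract, contact and consent usually fall one to two weeks before surgery.

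Staffing then follows the arm. Section 3.1 says that "based on their randomization, the study coordinator at each site will schedule either 1) a Healing Touch (HT) practitioner for the intervention group", with the control alternative being "a non-HT practitioner who will collect data for the control group". Section 4.3.1 repeats the order: "After being randomized into the intervention group or control group, and based on their scheduled delivery date, the study site coordinator will schedule the subject", with the kind of session set by the arm.

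The baseline comes last before the session. For the intervention arm, section 3.1 reads: "For the intervention group, the HT practitioner will verify consent. Then they will ask the woman to complete baseline measurements of pain and anxiety". The same practitioner then gives the treatment. For the control arm, section 3.2 has "a member of the research team, who may or not be a HT practitioner, will verify consent", followed by: "Then they will ask the woman to complete baseline measurements of pain and anxiety". Quiet time is introduced after that.

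Section 3.4.1 defines the outcome: "Primary outcomes will include the differences between the intervention and control groups' pre-/postintervention levels of pain", and likewise for anxiety. The hypotheses in section 1.2 speak of scores after the session. Section 4.2 gives an unadjusted two-sample t-test and does not say whether it is applied to change scores or post scores.

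No section describes blinding of the woman, a collector unaware of the arm, a score taken before allocation, or the moment at which the woman learns her arm.

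**The concern.** Both primary outcomes are self-reported, and anxiety in particular may respond to what a person expects to happen next. A woman who knows or guesses that she is about to receive Healing Touch, and one who knows or guesses that she will have quiet rest, may give their starting scores in different frames of mind. If the outcome is the change from that starting score, a difference that arose before any treatment is counted as part of the treatment effect.

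The direction is open. Scores reported higher to a practitioner before treatment would create an apparent benefit, while anticipatory calm would hide a real one. Aims 1 and 2 both depend on this comparison. A neutral collector after the session would not repair it, because the problem lies in the starting score. Nor could it be corrected afterwards, since neither its size nor its sign would be known.

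**Working it through.** **The plan's own figure.** Section 4.1 gives alpha 0.05 two-sided, power 0.80, d = 0.5 and equal allocation. For a two-sample t-test with n per arm, the noncentrality is d × √(n/2) on 2n − 2 degrees of freedom. With n = 64 this is 0.5 × √32 = 2.83, the critical value is 1.979 on 126 df, and the power is 0.801. With n = 63 the power is 0.795. So 64 per arm, 128 in total, reproduces.

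**How a baseline shift enters the result.** Define improvement as pre minus post. Let expectation raise the Healing Touch arm's mean pre score by b points relative to control, and let a fraction p of that shift persist to the post score. The bias in the difference in mean change is b × (1 − p).
- p = 0 (the shift is in the baseline only): the bias is b.
- p = 1 (the shift persists wholly): the bias is 0.
- Test on post scores alone, p = 0: the bias from this mechanism is 0.

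**Assumptions.** The documents give no SD and no basis for b. I assume scores on a 0-10 scale, a change-score SD of 1.5, 2 or 2.5 points, b of 0.25 or 0.5 points, p = 0, and 64 per arm. The standardized bias is b/SD. The rejection probability comes from the noncentral t with noncentrality (b/SD) × √32.

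The last column takes a true standardized effect of 0.5 on the change score and a shift in the opposite direction, so the test sees 0.5 − b/SD.

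| b (points) | SD | b/SD | Rejection, no true effect | Power, opposite shift |
|---|---|---|---|---|
| 0.25 | 1.5 | 0.167 | 15.5% | 46% |
| 0.25 | 2.0 | 0.125 | 10.8% | 56% |
| 0.25 | 2.5 | 0.100 | 8.7% | 61% |
| 0.50 | 1.5 | 0.333 | 46.5% | 15% |
| 0.50 | 2.0 | 0.250 | 28.9% | 29% |
| 0.50 | 2.5 | 0.200 | 20.2% | 39% |

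The nominal values are 5% and 80%. A normal approximation puts the upper ends slightly higher, near 16% and 47%. A shift of 0.1 points gives about 6 to 7%. If half of a 0.5-point shift persists to the post score, the 0.25-point rows apply.

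**Choice of analysis.** In raw-score SD units, take b = 0.2 and a pre-post correlation ρ = 0.5 (both assumed).
- Change score: bias = b/√(2(1 − ρ)) = 0.2/1 = 0.200, rejection 20.2%.
- Baseline-adjusted analysis: bias ≈ ρb/√(1 − ρ²) = 0.1/0.866 = 0.115, rejection about 9.9%.
- Post score alone: 5% with respect to this mechanism.

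With ρ from 0.3 to 0.7, the change-score figure for b = 0.2 runs from 15.8% to 30.5%.

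**Sample size.** Recruiting up to 160 does not help. At 80 per arm, a bias of d = 0.25 gives about 35% rejection instead of 29%.

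**The case against.** A reader might infer that the woman has been told her arm before she gives the baseline. The documents do not say so. In sections 3.1 and 3.2 the order is consent check, baseline, session, and quiet time is introduced only after the control baseline. Much of a sound sequence is already written; what is missing is when the arm is disclosed. This stands, so her knowledge must be treated as a possibility.

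A reader might also infer that the collector's role reveals the arm. Section 3.1 says the control collector is not a Healing Touch practitioner, but section 3.2 allows one, and practitioners may be registered nurses in the same system. Nothing says the visitor announces a role. This stands too. What can be said is that the collector knows the arm, because that person runs the session. One visible cue exists: the privacy text in section 3.1 has intervention staff ask about a do-not-disturb sign and notes that the sign may show the subject is receiving the intervention. Whether that question precedes the baseline is not stated.

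A third tempting reading is that any baseline shift passes in full into the result. That requires a change-score analysis and a shift confined to the baseline. Section 3.4.1 points towards change, but section 1.2 reads as post scores and section 4.2 is silent. Over about 15 minutes, expectation may well persist and cancel in part or in whole.

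Finally, the assumed shift drives every figure and has no source in the documents. This is correct, and the figures serve only as illustration.

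**Conclusion.** The point holds in a conditional form. The text establishes that allocation and arm-based staffing precede the baseline, that the person collecting it runs the session and so knows the arm, and that no step withholds the arm from the woman until it is recorded. The text does not establish that she knows her arm, that her score moves, or that the pre score enters the primary test.

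If all three hold and the shift is confined to the baseline, a 0.25-point shift would raise the false-positive rate from 5% to about 9 to 15%, and a 0.5-point shift to about 20 to 46%, for an assumed change-score SD of 1.5 to 2.5 and 64 per arm. A shift of the opposite sign would cost power instead. No single figure should be read as the trial's actual error rate.

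This is a plausible bias in self-reported primary outcomes that can be reduced at almost no cost. It is not a demonstrated flaw in the result.

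**What to change.** Amend sections 3.1 and 3.2 and the scheduling text in section 4.3.1 to state the following order:
1. The woman is not told her arm at scheduling.
2. At the bedside, the visitor reconfirms consent to the randomized study, using one identical neutral script in both arms that names neither role nor arm.
3. The woman completes the pain and anxiety baseline herself and the form is closed.
4. Only then is the arm disclosed, the do-not-disturb and visitor questions are asked, and the session starts.

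Reconcile sections 3.1 and 3.2 on who may collect control-arm data. State in section 4.2 whether the primary test uses change or post scores, since this decides whether the mechanism matters.

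The cost is wording and a short script; the visit, staff and sample size stay the same. The consent reconfirmation needs care, because it now takes place before the arm is named, and the do-not-disturb and visitor questions move to after the baseline form. Protection is partial: some women will guess their arm, staff remain aware of it, and unblinded reporting after the session is not addressed.
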